5.7.2. Adverse Events

Adverse events (AEs) will be summarized by MedDRA System Organ Class (SOC) and PT, classified from verbatim terms. The incidence and percentage of patients with at least 1 occurrence of a PT will be included, according to the most severe National Cancer Institute Common Terminology Criteria for Adverse Events (NCI-CTCAE) Version 4.0 grade.

If more than 1 AE is recorded for a patient within any PT, the patient will only be counted once on the most severe grade. Missing classifications concerning study treatment relationship will be considered as related to study treatment.

A treatment-emergent adverse event (TEAE) is defined as an event that first occurred or worsened between the first dose of study treatment and 30 days after the last dose of study treatment and related serious AEs (SAEs) reported beyond 30 days after the last dose of study treatment.

5.7.2.1. Overall Summary of Adverse Events

An overall summary of AEs will be provided to summarize the following categories using frequency counts and percentages:

- patients with at least 1 TEAE, or SAE
- deaths
- subjects who discontinued study treatment due to AE
- treatment-emergent adverse event related to study treatment
-

5.7.2.2. Treatment-Emergent Adverse Events

The following summaries of TEAEs will be provided and repeated for events deemed by the investigator to be possibly related to study medication:

- by PT

- by SOC and PT, and by maximum CTCAE grade

A patient listing of all AEs will be provided.

5.7.2.3. Adverse Event of Special Interest

Adverse events of special interest (AESI) include events related to arterial thromboembolism (ATE), venous thromboembolism (VTE), skin reactions (rash will be identified as a separate category as well as included under skin reactions), conjunctivitis, hypersensitivity/infusion related reaction (IRR), hypomagnesemia, and interstitial lung disease (pneumonitis). Each AESI is defined by a set of MedDRA PTs and the PT lists were identified by the medical and safety physicians for the compound based on the (blinded) review of all PTs (without looking at the number of patients/events for that PT) reported.

The incidence of treatment-emergent AESI will be summarized by AESI category and PT.

5.7.2.3.1. Thromboembolic Adverse Events

Thromboembolic AEs according to the AESI criteria outlined above are classified as arterial thromboembolic AE and venous thromboembolic AE. Treatment-emergent thromboembolic SAEs will be tabulated by overall, arterial thromboembolic AE, and venous thromboembolic AE. A listing of all treatment-emergent thromboembolic AEs will be generated.

In order to further assess the thromboembolic AEs observed in the study, an additional analysis examining possible risk factors for such events will be performed. Identification of these risk factors will be based on a literature search (Scappaticci et al. 2007; Khorana et al. 2008; Choueiri et al. 2010; Hurwitz et al. 2011; Petrelli et al. 2012; Lyman et al. 2013).

5.7.2.4. Consolidated Adverse Event

Consolidated AE categories include Anemia, Fatigue, Hypercalcaemia, Hyperkalaemia, Hypermagnesaemia, Hyponatraemia, Hyperphosphataemia, Hypocalcaemia, Hypokalaemia, Hypomagnesaemia, Hyponatraemia, Hypophosphataemia, Leukopenia, Neutropenia, and Thrombocytopenia. Each category contains PTs identified as clinically identical or synonymous, and PT lists were identified by the medical and safety physicians for the compound based on the (blinded) review of all PTs (without looking at the number of patients/events for that PT) reported.

The incidence of treatment-emergent consolidated AEs will be summarized by consolidated category and PT.

5.7.3. Deaths, SAEs, and Other Significant AEs

Reasons for deaths (study disease, AE [any AE, study treatment-related AE], etc.) will be summarized separately for 1) all deaths, 2) death on therapy, 3) deaths within 30 days of discontinuation of study therapy, 4) deaths on therapy or within 30 days of discontinuation of study therapy, and 5) deaths after 30 days of discontinuation of study therapy.

Serious adverse events will be summarized by SOC and PT, by maximum CTCAE grade, and by SOC and PT, and repeated for events deemed by the investigator to be possibly related to study medication. A listing of SAEs will be produced.

In addition, the following analyses will be performed:

- listing of adverse events leading to death
- listing of adverse events leading to study treatment discontinuations
- adverse events leading to study treatment dose modification by SOC and PT

Patients in Part A who experienced a DLT will be listed.

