Provided there is an acceptable safety profile in Part A of this study, Part B will be initiated, which will include a safety interim analysis after the first 15 evaluable patients have completed 2 cycles of study treatment (or otherwise discontinued study treatment). Patients with squamous and nonsquamous NSCLC who received the recommended abemaciclib dose for Part B in Part A will be taken into account for the safety interim analysis.

The final analysis for all outcomes will be performed approximately 5 months after completing enrollment of the study population.

A treatment cycle will be defined as 21 days. Study therapy, consisting of necitumumab plus abemaciclib will continue until there is a radiographic documentation of PD, toxicity requiring cessation, protocol noncompliance, or withdrawal of consent.

Terms used to describe the periods during the study are defined below:

- **Baseline:** begins when the ICF is signed and ends at the first study treatment (or at discontinuation, if no treatment is given).
- **Study Period:** begins at the first study treatment and ends at study completion. The study period does not include the continued access period.
  - **Study Treatment Period:** begins at the first study treatment and ends when the patient and the investigator agree that the patient will no longer continue study treatment. The date of this agreement is to be reported on the case report form (CRF) as the Date of Discontinuation from study treatment.
  - **Postdiscontinuation Follow-Up:** begins the day after the patient and the investigator agree that the patient will no longer continue study treatment.

*Short-term follow-up* begins the day after the patient and the investigator agree that the patient will no longer continue study treatment and lasts approximately 30 days.

[figure not shown]
*Long-term follow-up* begins the day after short-term follow-up is completed and continues until the patient's death or overall study completion.

- **Continued Access Period:** begins after study completion and ends at the end of trial. During the continued access period, patients on study treatment who continue to experience clinical benefit and no undue risks may continue to receive study treatment until one of the criteria for discontinuation is met. The continued access period includes continued access follow-up.

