#### **9.3.2.2.3.1.7. Cardiorespiratory Disorders**

An increased frequency of cardiorespiratory arrest or sudden death was observed with necitumumab. Cardiorespiratory arrest or sudden death was reported in the pivotal Study JFCC (SQUIRE) in 2.8% (15/538) of patients treated with necitumumab plus gemcitabine and cisplatin compared to 0.6% (3/541) of patients treated with chemotherapy alone. Twelve of the 15 patients died within 30 days of the last dose of necitumumab and had comorbid conditions, including history of chronic obstructive pulmonary disease (n=7), hypertension (n=5), hypomagnesemia (n=4), and coronary artery disease (n=3). Eleven of the 12 patients had an unwitnessed death.

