### **12.2.9. Safety Analyses**

All safety summaries and analyses will be based upon the Safety Population as defined in Section [12.2.2](#).

Overall exposure to study drugs, the numbers of patients completing each cycle, and the dose intensity will be summarized using descriptive statistics. The number of patients with any dose adjustment will be presented for entire treatment period. The number of patients with dose reductions, dose delays, or dose omissions will also be summarized, as will the reasons for dose adjustments.

An overall summary of AEs will be provided for AEs deemed by the investigator to be possibly related to study treatment, and repeated for events regardless of study drug causality.

A treatment-emergent adverse event (TEAE) is defined as an event that first occurred or worsened between the first dose of study treatment and 30 days after the last dose of study treatment and related SAEs reported beyond 30 days after the last dose of study treatment.

The number of patients who experienced a TEAE, SAE, AE related to study treatment, died, or discontinued from the study therapy due to an AE will be summarized.

Common Terminology Criteria for Adverse Events v 4.0 will be used to report AEs by CTCAE terms.

Laboratory and non-laboratory CTCAEs will be summarized by CTCAE term and maximum CTCAE grade, including the total for maximum Grade 3 and above. These summaries will be provided for events deemed by the investigator to be possibly related to study treatment and repeated for events regardless of causality.

MedDRA Version 17.0 (or higher) will be used when reporting AEs by MedDRA terms.

Treatment-emergent adverse events will be summarized by System Organ Class (SOC) and by decreasing frequency of Preferred Term (PT) within SOC.

Reasons for death will be summarized separately for on-therapy and within 30 days of last dose of study drug. Serious adverse events will be summarized by PT.

Hospitalizations and transfusions during the study treatment period or during the 30-day short-term follow-up period will be summarized.

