5.7.5. Laboratory Evaluations

Laboratory results will be converted to standard (SI) units, as referenced in the NCI-CTCAE v.4.0. Laboratory results not corresponding to a NCI-CTCAE v.4.0 term will not be graded.

Shift tables showing the change from baseline to the worst CTCAE toxicity grade (first dose up to 30 days after the last dose of study treatment) will be presented.

Laboratory results will also be presented in a data listing to include a flag for values outside of the laboratory normal range. A listing of patients who had laboratory toxicities of CTCAE Grade 3 or greater will be presented.

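### SAP 5.7.3 counts 30-day deaths from an undefined discontinuation date, while Protocol 12.2.9 and the SAP's other 30-day safety windows count from the last dose

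*SAP*

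**What the plan says.** SAP 5.7.3 tabulates reasons for death in five groups. The first two are all deaths and deaths on therapy. The third is "3) deaths within 30 days of discontinuation of study therapy". The fourth pools the second and third groups, and the fifth holds the deaths later than that 30-day period. The SAP attaches no date to discontinuation of study therapy.

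The protocol's safety section (12.2.9) uses a different anchor: "Reasons for death will be summarized separately for on-therapy and within 30 days of last dose of study drug".

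The only place that gives discontinuation a date is the description of the study treatment period in Protocol 8.1. The period ends when patient and investigator agree to stop, and "The date of this agreement is to be reported on the case report form (CRF) as the Date of Discontinuation from study treatment". That is a decision date, not a dosing date.

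Elsewhere the SAP counts from dosing. A treatment-emergent event is one that "first occurred or worsened between the first dose of study treatment and 30 days after the last dose of study treatment", with related serious events added after that (5.7.2). Laboratory shifts run from "first dose up to 30 days after the last dose of study treatment" (5.7.5). Transfusions (5.8.3) and hospitalizations (5.9) also close 30 days after the last dose.

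**The concern.** As written, the SAP need not produce the death table that Protocol 12.2.9 asks for. The death table is also the exception among the SAP's own 30-day safety windows.

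Deaths on or soon after treatment are a key safety count for this combination, and a reader will set that count beside the treatment-emergent tables. If the anchors differ, a death can appear as early in one table while its fatal event is absent from the other, and nothing in the output would explain why.

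**Working it through.** There is no stated figure to reproduce; the check compares the windows.

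**Inputs**
- Window length: 30 days (SAP 5.7.3, Protocol 12.2.9).
- Abemaciclib may be held for up to 14 days for recovery from toxicity (Protocol 9.3.2.2.1).
- A patient whose abemaciclib has been stopped may continue on necitumumab alone (text under Table JFCU.9.2).
- Necitumumab is to be discontinued once its delay exceeds 6 weeks, or 42 days, after Day 1 of the latest cycle (Protocol 9.3.2.2.2).
- The Day 8 necitumumab dose can be omitted (Protocol 9.3.1).

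**Assumptions.** Discontinuation of study therapy means the decision date of Protocol 8.1, for all study drug. Let L be the last dose of either drug, S the decision date and g = S − L, with g ≥ 0.

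**Formula.** The SAP death window ends g + 30 days after the last dose. The last-dose window ends at day 30. The two disagree over g days.

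| Situation | g (days) | SAP window ends, days after last dose | Last-dose window ends |
|---|---|---|---|
| Decision on the day of the last dose | 0 | 30 | 30 |
| Neither drug given for 14 days (abemaciclib hold limit) | 14 | 14 + 30 = 44 | 30 |
| Necitumumab alone, last dose Day 8, decision 42 days after Day 1 | 42 − 7 = 35 | 35 + 30 = 65 | 30 |
| Necitumumab alone, Day 8 omitted, decision 42 days after Day 1 | 42 | 42 + 30 = 72 | 30 |

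**Direction.** Suppose a death occurs on date D with D − L ≤ 30. Since S ≥ L, D ≤ L + 30 ≤ S + 30. The death is therefore either before the decision or within 30 days of it, and SAP category 4 contains it. The SAP window can only add deaths.

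**What is added.** Take g = 35 and a fatal event that begins 20 days after the decision, with death before day 30 after the decision. The event begins 35 + 20 = 55 days after the last dose. The death is in SAP category 3. It is outside the protocol's window, and the event is not treatment-emergent unless it is a related serious event.

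With the anchor moved to the last dose, all these windows close at day 30 and the disagreement is 0 days.

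**The case against.** Several points on the other side stand.

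- **The decision date is an inference.** The SAP never says that it means that date; the reading comes from a case report form field described in Protocol 8.1. What is certain is that the anchor is undefined and worded differently from the protocol. The 44, 65 and 72 days hold on one reading only.
- **The decision date has a rationale.** Short-term follow-up starts the day after the decision (Protocol 8.1), and all adverse events are collected through it (Table JFCU.10.1). Protocol 12.2.9 itself summarizes hospitalizations and transfusions over that follow-up.
- **Long gaps need unusual circumstances.** The protocol says the abemaciclib schedule should be maintained when necitumumab is altered for its own toxicity, and that necitumumab should not be delayed for abemaciclib toxicity (end of 9.3.2.2.3). A hold of one drug while the other continues creates no gap from the last dose of either. The 65 and 72 day cases also need abemaciclib already stopped and the decision taken only at the necitumumab limit.
- **Little is hidden.** The SAP lists all adverse events, serious events and events leading to death. Later related serious events still count as treatment-emergent, so that part of the mismatch is confined to fatal events judged unrelated.

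Protocol 12.2.1 lets the SAP make minor changes or clarifications. That does not settle the matter, because the SAP neither identifies nor explains a change here. Its revision history mentions only interim efficacy analyses and a general alignment with standard output shells.

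Two stronger readings are tempting but unsupported. A reader might infer that counting a death during a long hold as on therapy departs from the protocol. Protocol 12.2.9 has an on-therapy category too, equally undefined, and the protocol's treatment period runs to the decision. A reader might also infer that the SAP spoils a comparison with the protocol's sudden-death figure, "Twelve of the 15 patients died within 30 days of the last dose of necitumumab" (9.3.2.2.3.1.7). Neither document plans that comparison. The figure concerns a specific event, timed from necitumumab, in a regimen with gemcitabine and cisplatin.

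**Conclusion.** The protocol and SAP conflict on the anchor of the 30-day death count, and the SAP's anchor is undefined. If it is the decision date, the SAP window equals the protocol's when there is no gap, and otherwise exceeds it by the gap: 14 days in the first hold case above and 35 to 42 days at the permitted extreme. These figures rest on the protocol's hold and delay limits and on the decision being recorded at those limits.

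The documents give no distribution of gaps, so the number of patients affected is unknown. It is probably small, because the two drugs are held independently. A reader might infer that early deaths would be lost; they would not be, as long as the decision does not precede the last dose.

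This is a matter of consistent safety reporting. It does not touch the primary analysis.

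**What to change.** In SAP 5.7.3, anchor categories 3 to 5 on the date of last dose of either study drug, as in Protocol 12.2.9 and the SAP's treatment-emergent definition. Define on therapy so that categories 2, 3 and 5 do not overlap and category 4 is the sum of 2 and 3. Without that definition, a death late in a long hold could be both on therapy and more than 30 days after the last dose.

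If the sponsor prefers a decision-date window to match short-term follow-up, the SAP should define the date, state that it departs from Protocol 12.2.9, and show both counts. If last dose was meant all along, one sentence settles it.

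The cost is a few lines of SAP text and a changed anchor date in one table program, or one further set of counts under the alternative. The last-dose dates are already needed for the exposure calculations in SAP 5.7.1, so no new data are required.

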5.7.4. Weight, Performance Status, and Vital Signs

5.7.4.1. Weight and ECOG Performance Status

Weight observed value and change from baseline will be presented by scheduled visit.

The ECOG performance status results will be summarized using frequency distributions for each scheduled visit, including also the best postbaseline value.

5.7.4.2. Vital Signs

Vital sign observed value and change from baseline will be presented by scheduled visit.

5.7.5. Laboratory Evaluations

Laboratory results will be converted to standard (SI) units, as referenced in the NCI-CTCAE v.4.0. Laboratory results not corresponding to a NCI-CTCAE v.4.0 term will not be graded.

Shift tables showing the change from baseline to the worst CTCAE toxicity grade (first dose up to 30 days after the last dose of study treatment) will be presented.

Laboratory results will also be presented in a data listing to include a flag for values outside of the laboratory normal range. A listing of patients who had laboratory toxicities of CTCAE Grade 3 or greater will be presented.

5.7.6. Electrocardiogram

Electrocardiogram (ECG) results will be listed.

5.8. Other Analyses

5.8.1. Pharmacokinetic (PK) Analyses

Pharmacokinetic (PK) analyses will be performed by Lilly PK according to a separate PK analysis plan.

5.8.2. Immunogenicity Analyses

The number and percentage of patients with positive anti-necitumumab response will be summarized. Additional efficacy and/or safety analyses may be performed in the subgroup of patients with positive anti-necitumumab responses, if appropriate.

5.8.3. Concomitant Therapy and Post-Study Anticancer Treatments

Prior and concomitant therapy will be summarized separately by frequency tables. A medication will be regarded as **prior** if it started within 28 days prior to first dose of study treatment and stopped prior to first dose of study treatment (medication stop date < first dose date). A medication will be regarded as **concomitant** if:

- it started on or after the date of first dose of study treatment and within 30 days after the date of last study treatment; or
- it started prior to first dose of study treatment but was ongoing at the time of the first dose of study treatment.

The numbers and percentages of patients reporting postdiscontinuation anticancer therapies will be provided overall, by type of therapy (surgery, radiotherapy, or systemic therapy), and by drug name.

Transfusions during the study treatment or within 30 days of the last dose of study drug will be summarized.

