### 7.1. Inclusion Criteria

Patients are eligible to be included in the study only if they meet **all** of the following criteria:

- [1] Histologically or cytologically confirmed NSCLC
  - Part A: NSCLC Stage IV (any type)
  - Part B: NSCLC Stage IV (squamous and nonsquamous)
- [2] Stage IV disease at the time of study entry (American Joint Committee on Cancer [AJCC] Staging Manual, 7th Edition [Edge et al. 2009])
- [3] Measurable disease at the time of study entry as defined by Response Evaluation Criteria in Solid Tumors Version 1.1 (RECIST 1.1) (Eisenhauer et al. 2009)
- [4] The patient must have progressed after platinum-based chemotherapy AND have received a maximum of 1 other prior chemotherapy for advanced and/or metastatic disease OR must be judged by the physician as ineligible for further standard second-line chemotherapy. Prior treatment with EGFR-TKI and ALK inhibitors is mandatory in patients whose tumor has EGFR-activating mutations or ALK translocations. Prior targeting agents and neoadjuvant/adjuvant therapies are permitted with the exception of CDK4/6-targeting agents or necitumumab.
- [5] The patient has tumor tissue available for biomarker analyses. The sample can be either 12 serially paraffin-embedded unstained tissue slides or a paraffin-embedded tissue block (see Section 10.3.2.2 for further details).
- [6] The patient has given written informed consent prior to any study specific procedures. Written consent may also be provided by a legal representative.
- [7] The patient is 18 years or older if required by local law or regulations.
- [8] The patient has resolution to Grade  $\leq 1$  by the National Cancer Institute Common Terminology Criteria for Adverse Events (NCI-CTCAE), Version 4.0, of all clinically significant toxic effects of prior chemotherapy, surgery, or radiotherapy (with the exception of alopecia).
- [9] The patient has an Eastern Cooperative Oncology Group performance status score of 0-1 (see [Attachment 4](#)).

[10] Have the following laboratory values:

- hematologic: absolute neutrophil count  $\geq 1.5 \times 10^9/L$ , platelets  $\geq 100 \times 10^9/L$ , and hemoglobin  $\geq 9$  g/dL. Transfusion of blood products (including platelets or red blood cells) or administration of colony stimulating factors (including G-CSF, GM-CSF, or recombinant erythropoietin) within 4 weeks prior to Cycle 1 Day 1 are not allowed.
- serum albumin  $\geq 25$  g/L

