## **9.5. Concomitant Therapy**

Appropriate documentation of all forms of premedications, supportive care, and concomitant medications must be captured at each visit in the CRF. Concomitant medications and supportive care therapies must also be documented at the time of discontinuation and at the 30-day short-term follow-up visit.

With the exceptions listed in the sections below, no other chemotherapy, experimental medications, other anticancer therapy, immunotherapy, hormonal cancer therapy, radiation, surgery for cancer, or experimental medications will be permitted while patients are on study treatment. Palliative radiotherapy, unless required due to progressive disease, is permitted during the study.

The results from an in vitro human recombinant cytochrome P450 (CYP) phenotyping study indicate that oxidative metabolism of abemaciclib is primarily catalyzed by CYP3A4. However, the extent of oxidative metabolism responsible for the systemic clearance of abemaciclib in humans is presently unknown. Based on these in vitro findings, grapefruit juice as well as inducers (for example, phenytoin or carbamazepine) and strong inhibitors of CYP3A4 should be

substituted or avoided if possible ([Attachment 8](#)). In addition, in vitro studies in primary cultures of human hepatocytes indicate that abemaciclib might inhibit the metabolism of CYP2B6 substrate drugs in vivo in human. Based on this finding, sensitive CYP2B6 substrates such as bupropion and efavirenz should be substituted or avoided if possible ([Attachment 8](#)).

Bisphosphonates or denosumab for bone metastasis are permitted.

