## **Attachment 1. Protocol JFCU Study Schedule**

---

Study Schedule, Protocol I4X-MC-JFCU

Perform procedure as indicated in the following schedules.

Baseline Schedule, I4X-MC-JFCU

		Baseline				
			BL			
			0			
		Relative day within a cycle	≤21	≤14	≤7	
Procedure Category	Protocol Section	Procedure				Comments
Study Entry/ Enrollment	13.1	Informed consent form signed				ICF must be signed prior to performing any protocol-specific tests/procedures.
	7.1, 7.2	Inclusion/exclusion evaluation	X			
Medical History	12.2.3	Initial history/preexisting conditions		X		
	12.2.3	Historical illnesses		X		
		Habits assessment		X		Smoking
Physical Examination		Height		X		
		Weight		X		
		Blood pressure/pulse/temperature		X		
	Att. 4	ECOG performance status		X		
Efficacy Assessment	10.1.1	Radiologic imaging/Tumor Assessment (according to RECIST v1.1)	X			A contrast CT scan or MRI of the brain will be performed if the patient is known to have CNS metastasis.
Adverse Events	10.2.1	AE collection and CTCAE grading	X			Data on SAEs that occur before the end of trial will be stored in the collection database and the Lilly Safety System.
Concomitant Medications	9.5	Concomitant medication notation	X			

		Baseline				
		Cycle	BL			
		Visit	0			
		Relative day within a cycle	≤21	≤14	≤7	
Procedure Category	Protocol Section	Procedure				Comments
Laboratory/ Diagnostic Tests	Att. 2	Hematology (central)		X		
	Att. 2	Chemistry (central)		X		
	Att. 2	Coagulation (central)		X		
	Att. 2	Urinalysis (local)		X		
	Att. 2	Pregnancy test (central)		X		In women of childbearing potential
	10.3.2.1	Whole blood for pharmacogenetic analysis	Refer to Attachment 7			
	10.3.4	PK sampling (central)	Refer to Attachment 7			
	10.3.3	Immunogenicity: Anti-necitumumab antibodies	Refer to Attachment 7			
	10.3.2.3	Plasma sample for Biomarker Analysis	Refer to Attachment 7			
	10.3.2.2	Tumor tissue sample	X			To meet study eligibility criteria, and therefore mandatory for study participation, patients must have available FFPE tumor sample. Previously archived Stage IV NSCLC tissue from the initial diagnosis may be used but the most recent sample is preferred (for example, at relapse). The sample can be either 12 serially cut unstained sections or a tissue block (preferred). See Section 10.3.2.2 for further details.
10.2.2.1	ECG (local)		X			

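### The 28-day limit for prior medication is set on the start date, so a longer-standing drug stopped before first dose appears in neither the prior nor the concomitant table

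*SAP*

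**What the plan says.** SAP 5.8.3 announces two tables: "Prior and concomitant therapy will be summarized separately by frequency tables". It then sets the membership rules.

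- **Prior:** a medication qualifies "if it started within 28 days prior to first dose of study treatment and stopped prior to first dose of study treatment". The SAP spells out the second condition as "medication stop date < first dose date". Both conditions must hold.
- **Concomitant, first route:** "it started on or after the date of first dose of study treatment and within 30 days after the date of last study treatment".
- **Concomitant, second route:** "it started prior to first dose of study treatment but was ongoing at the time of the first dose of study treatment".

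There is no third category. Protocol 12.2.4 says only that concomitant medications will be summarized for the safety population, and it does not define prior medication. SAP 5.3 has a rule for incomplete start dates of concurrent therapies. When the known month (or, if only the year is known, the year) precedes that of first treatment, the start is set to the date of informed consent.

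**The concern.** A 28-day limit on a prior-medication table is naturally a recency window: it should pick out what the patient was taking shortly before dosing. Here it picks out what the patient began taking shortly before dosing. A one-day course on Day -1 is tabulated, but a drug taken daily for two years and stopped on Day -1 is not.

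The protocol itself gives reasons to want recent use on display. Inclusion criterion 10 is framed by recent use: blood-product transfusions or colony-stimulating factors "within 4 weeks prior to Cycle 1 Day 1 are not allowed". Protocol 9.5 says that "oxidative metabolism of abemaciclib is primarily catalyzed by CYP3A4" and asks that inducers and strong inhibitors be substituted or avoided where possible. A patient moved off a long-term drug of that kind before dosing is someone a reader would expect to find in the prior table. What is at stake is the completeness of that table and its internal consistency.

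**Working it through.** The plan gives no figure to reproduce; this is a check of a classification rule.

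**Notation.** Let S be the start day and E the stop day, numbered as in SAP 5.2: first dose is Day 1 and the day before it is Day -1. A drug whose stop date is the day of first dose is taken as ongoing at first dose.

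**The rules in SAP 5.8.3.**
- Prior: -28 ≤ S ≤ -1 and E ≤ -1.
- Concomitant: S from Day 1 to 30 days after last treatment; or S ≤ -1 and E ≥ Day 1.

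**The gap.** Take any drug with S ≤ -1 and E ≤ -1. The first concomitant route fails because S is before first dose. The second fails because E is before first dose. Prior fails whenever S ≤ -29. So every drug with a complete start date on or before Day -29 and a stop on or before Day -1 is in neither table. Those stopped before Day -28 are outside any 28-day window and are reasonably left out. Those stopped from Day -28 to Day -1 are the ones lost.

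| Start | Stop | Prior now | Concomitant now | Prior if limit is on use |
|---|---|---|---|---|
| -730 | -3 | no | no | yes |
| -40 | -10 | no | no | yes |
| -29 | -1 | no | no | yes |
| -28 | -1 | yes | no | yes |
| -10 | -3 | yes | no | yes |
| -730 | day of first dose or later | no | yes | no |
| -730 | -40 | no | no | no |

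**Exhaustive check.** With start days from -365 to -1 and stop days from -28 to -1, the unclassified pairs are those with starts from -365 to -29 (337 days) and any of the 28 stop days: 337 × 28 = 9,436. With the limit on use, none of these remains unclassified. Prior and concomitant never overlap under either rule, because one needs a stop before first dose and the other does not allow it for an earlier start. These are date combinations and say nothing about how many patients are affected.

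**Partial start dates.** Suppose the SAP 5.3 imputation is applied, and assume consent falls within 28 days before first dose (the protocol synopsis gives a 21-day baseline period). A long-standing drug stopped on Day -3 whose start is imputed to consent on Day -21, -14 or -7 then satisfies -28 ≤ S ≤ -1 in each case and is classed as prior. The same drug with a full start date is dropped, so the better-documented record is the one omitted.

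**The case against.** The strongest reply is that nothing of consequence rests on this table.

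- **Eligibility.** A reader might infer that a growth factor taken from Day -40 to Day -10, in breach of criterion 10, would go unreported. The documents do not support that. SAP 5.4 lists failure to meet inclusion or exclusion criteria as a predefined important protocol violation, summarized by type.
- **Cycle 1 PK and DLTs.** A reader might also infer that omitting a withdrawn CYP3A4 inducer or inhibitor distorts these results. No specified analysis uses the table: PK follows a separate plan (SAP 5.8.1), and DLTs are defined by Cycle 1 toxicity (protocol 9.3.2.1) and listed by patient (SAP 5.7.3). The protocol does not require withdrawal of such drugs, and Attachment 8 says its list does not preclude their use. Any that continue are concomitant and tabulated. Protocol 9.5 adds that the share of clearance due to oxidative metabolism is unknown.
- **Other summaries.** Previous systemic anticancer therapy (SAP 5.5.2) and preexisting conditions (SAP 5.5.3) are reported separately. The prior-medication table is an SAP addition that protocol 12.2.4 does not promise.

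All of this stands as a limit on the consequences. None of it closes the gap: no other section classifies these drugs, and a table that is produced should contain what its title implies.

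**Conclusion.** The point holds as a defect in a stated rule, of minor weight. For complete start dates, the omission of drugs begun before Day -28 and stopped from Day -28 to Day -1 follows directly from the text. For partial start dates, the inconsistency depends on two assumptions: that SAP 5.3 is applied to these drugs, and that consent falls within the 28 days. It would therefore be wrong to say that every such medication is lost.

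The size cannot be stated, because the documents give no count. Nor do they support saying that most long-term drugs stopped at screening fall in the gap, since nothing says such drugs are routinely stopped then. The loss falls mainly on non-anticancer drugs. The primary endpoint, alpha and power are untouched.

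**What to change.** In SAP 5.8.3, define prior medication as any medication taken at any time in the 28 days before first dose and stopped before first dose. In terms of dates, the stop falls from Day -28 to Day -1 and the start is any earlier or equal date. Leave the concomitant definition as it is. Full and partial start dates before first dose then give the same answer, because the start date no longer decides membership.

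The cost is a short phrase in the SAP and the matching line of table code, made before database lock. It needs no protocol amendment, no new data and no change to patient care. It recovers only what is recorded. Protocol Attachment 1 schedules "Concomitant medication notation" at baseline, and protocol 8.1 starts baseline at consent. If consent falls at the start of a 21-day baseline, the first 7 days of the window (28 − 21) precede it. The documents do not show whether drugs stopped in those days are collected, so a table footnote should say which records the summary draws on.
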